This exploratory project brings together an interdisciplinary team to leverage decades of research on behavior change from exposure theory to design and pilot-test an EBIS to target clinician-level anxiety about SSAI use to improve SSAI implementation for two gold-standard SSAIs: the Columbia Suicide Severity Rating Scale (CSSRS; Posner et al., 2011) and the Safety Planning Intervention (SPI; Stanley & Brown, 2008).

In partnership with a team of clinicians, setting leaders, implementation scientists, and suicide experts we propose to:

Aim 1: Develop an EBIS to reduce clinician anxiety and bolster self-efficacy to deliver SSAI. The EBIS will leverage exposure-based therapies to manage core clinician fears and anxiety related to suicide in high-risk patient encounters. Using participatory design methods, design and adaptation will be conducted collaboratively with key stakeholders.

Aim 2: Iteratively refine the EBIS in pilot field-testing using rapid cycle prototyping. We will engage 20 clinicians who will receive pilot iterations of EBIS; qualitative feedback will inform further refinement.

Aim 3: Test acceptability, feasibility, and preliminary effectiveness of the EBIS compared to Implementation as Usual (IAU) to target SSAI implementation mechanisms and implementation outcomes in a pilot randomized clinical trial with 40 clinicians. EBIS acceptability and feasibility will be measured via surveys and interviews. Exploratory analyses will examine impact of both conditions on putative implementation mechanisms (clinician anxiety, self-efficacy) and outcomes (SSAI adoption, fidelity). We will triangulate implementation outcomes via surveys, chart-stimulated recall, and standardized role plays coded by objective observers. Qualitative interviews with clinicians will further explore implementation outcomes and identify which changes to the EBIS are needed before confirmatory trials.

Note that our objective in the Aim 3 trial is to test whether the EBIS approach to clinician training results in better clinician self-efficacy and increased use of and fidelity to the gold standard SSAIs of interest in this study (the CSSRS and SPI), which are currently already the recommended practice in many City of Philadelphia agencies. We are *not* testing any patient level

outcomes in this exploratory study nor are we recruiting or interacting with any patients in this study.

BACKGROUND:

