In sum, clinician anxiety and low self-efficacy are key implementation barriers to SSAI use but have not been implementation strategy targets. We will target these mechanisms by developing and pilot-testing an exposure-based implementation strategy (EBIS) for implementing the following evidence-based SSAs: the Columbia Suicide Severity Rating Scale (CSSRS) screener and assessment tool²² and the Safety Planning Intervention (SPI).²⁴ Data will inform an R01 to test EBIS at scale.

CHARACTERISTICS OF THE STUDY POPULATION:

1. Target Population and Accrual:

Aim 1: Aim 1 is a preparatory aim and does not involve human subjects research.

Aim 2: Aim 2 participants will be community clinicians (n = 20) recruited from any local community mental health clinics in the Philadelphia region.

Aim 3: Aim 3 participants are community clinicians (n = 40) recruited from 3-5 community mental health clinics in the City of Philadelphia.

2. Key Inclusion Criteria:

Aim 1: N/A

Aims 2 and 3: Participants must be:

- 1) Practicing mental health clinicians in the City of Philadelphia who provide direct mental health services to a treatment-seeking population.
**This may include mental health clinicians who are both licensed or unlicensed (i.e., intern or trainees seeking licensure or practicing under another provider's license). If the participant is a practicing clinician at a clinic from which we recruit, they will be eligible for the study. Potential licensures may include but are not limited to:
 - a. Licensed Family and Marriage Therapist (LMFT)
 - b. Licensed Clinical Social Worker (LCSW)
 - c. Licensed Social Worker (LSW)
 - d. Licensed Professional Counselor (LPC)
 - e. Licensed Mental Health Counselor (LMHC)
 - f. Licensed Clinical Professional Counselor (LCPC)
 - g. Licensed Professional Clinical Counselor of Mental Health (LPCC)
 - h. Licensed Clinical Mental Health Counselor (LCMHC)
 - i. Licensed Mental Health Practitioner (LMHP)
 - j. Clinical Psychologist (Licensed PsyD or PhD)
- 2) Proficient in the English language
- 3) Have access to a computer with internet connectivity

3. Key Exclusion Criteria:

Aim 1: N/A

Aims 2 and 3: Participants will be excluded if they do not see any mental health patients that are at risk for suicide (e.g., they screen out all high-risk patients for their individual practice). Participants will not be excluded based on sex, demographics, and or past experience.

4. Subject Recruitment and Screening:

Aim 1: N/A

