- **Chart Stimulated Recall (CSR).** An established technique for examining clinician decision-making and clinical processes beyond what can be determined from chart review or self-report alone. A trained research team member will review the clinician's caseload with them for the past clinic week and ask them brief questions (no more than 5 minutes) related to the clinician's suicide-related practices (e.g., "Did you conduct a screen for suicide risk? How did you screen for risk? If risk was present, was a full CSSRS/SPI administered?). This will be administered at Time 1 and 3-4. No identifiable patient information is collected during the CSR and the study staff will not ever view the chart directly. Clinicians are instructed to refrain from sharing any identifiable patient details during the CSR administration.
 - o This measure was previously reviewed and approved by the IRB.
- **Brief Role Plays.** Participants will receive a vignette and prepare for a 45-60-minute role play, during which they will be asked to complete an SPI with a patient who was determined to be at-risk for suicide following CSSRS administration with a trained actor. Role plays will be audio-recorded and coded for competence with the Safety Planning Intervention Rating Scale (SPIRS). This will be administered at Time 3 and Time 4.

- An example of the procedures and coding scheme for the role play are included for the IRB's review.

Secondary Outcomes: Additional Mechanisms of Interest

- **Self-Perceived Knowledge & Attitudes About Suicide Scale.** Selected subscales (Knowledge, Attitudes) of the Short Survey on Knowledge, Self-Confidence, and Attitudes Towards Suicidal Behavior will assess a clinician's perceived knowledge about suicide and how to intervene. This will be administered at Time 1- 4.
 - This measure was previously reviewed and approved by the IRB.
- **Clinician Attitudes Toward Safety Planning.** A 12-item questionnaire assessing clinician attitudes and beliefs about the use of safety planning interventions in clinical practice with suicidal patients. This will be administered at Time 1- 4.
 - This measure was previously reviewed and approved by the IRB.
- **SSAI Intentions and Determinants of Intention.** Established question stems from behavioral science using items on a 7-point scale asking how willing and how likely one is to use SSAs as well as attitudes and perceived norms of SSAI use. This will be administered at Time 1- 4.

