 - This measure was previously reviewed and approved by the IRB.
- **Clinician Demographics.** Brief questionnaire about clinician demographic (e.g., age, sex) and professional characteristics (e.g., years of experience, theoretical orientation, caseload descriptions), work setting, and a question about the clinician's person experience with suicide (e.g., "Have you ever had a client die by suicide while under your care?"). This will be administered at Time 1.
 - This measure was previously reviewed and approved by the IRB.
- **Anxiety Sensitivity Index (ASI-3).** Questionnaire about the clinician's physical, cognitive, or social concerns about anxiety. This will be administered at Time 1.
 - This measure was previously reviewed and approved by the IRB.
- **Organizational Innovation Specific Capacity for Suicide Prevention Evidence-based practices (OISCSE).** Questionnaire about the organizational policies, procedures, and practices within the clinician's organization to observe potential factors that could influence use of SSAI's. This measure has 14-items on a Likert scale plus a yes or no question to query any additional factors about the clinician's organization not mentioned in the first 14-items. If the clinician responds positively, they are asked an additional open response question. This measure was adapted from a previously developed measure to assess policies and procedures needed to support exposure therapy delivery, guided by responses to qualitative interviews completed in Aim 2 of this study and items from the Zero Suicide Organizational Self-Study in collaboration with suicide prevention and implementation science experts.
 - A copy of this measure is included for the IRB's review.

Table 2. Assessment Schedule for Aim 3

Outcome	Measure	T1	T2	T3	T4
Primary Outcomes					
EBIS Acceptability	Acceptability of Intervention Measure; Qualitative Interview (T4 only)		X		X
EBIS Feasibility	Feasibility of Intervention Measure; Recruitment/Retention statistics		X		X
Secondary Outcomes					
Target Implementation Mechanisms					
Clinician Anxiety	Subjective Units of Distress Scale; ⁷¹ Suicidal Patient Comfort Survey ⁵⁵ ; Anxiety Sensitivity Index (ASI-3) (Time 1 only)	X	X	X	X
Clinician Self-efficacy	Established question stems ⁸¹	X	X	X	X
Implementation Outcomes					
SSAI use (CSSRS, SPI)	Chart Stimulated Recall ⁸²	X		X	X
SPI Fidelity	Role Play coded w/ SPIRS			X	X
Additional Implementation Mechanisms of Interest					

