SSAI Knowledge	Self-Perceived Knowledge About Suicide Scale ⁸³	X	X		X
SSAI Attitudes	Attitudes Toward Suicide Prevention; ⁸⁴ Clinician Attitudes Toward Safety	X	X	X	X

	Planning ⁸⁵				
SSAI Intentions	Established question stems ⁸¹		X	X	X X
SSAI Norms	Established question stems ⁸¹		X	X	X X
Demographics	Demographics survey		X		
Organizational Factors	Organizational Innovation Specific Capacity for Suicide Prevention Evidence-based practices (OISCSE)		X		
T1=baseline. T2=post-training. T3=2-week. T4=12-week follow-up.					

2. Group Modifications:

Aims 1 and 2: N/A

Aim 3: After consenting to participate, clinicians will be randomly assigned to one of the two implementation conditions; the measurement battery will be identical for clinicians in each condition, with the exception that qualitative interviews for clinicians randomized to the EBIS condition will include several additional questions about their specific experience with EBIS.

3. Method for Assigning Subjects to Groups:

Aim 1: N/A

Aim 2: No participants will be randomized as a part of Aim 2 activities.

Aim 3: Clinician participants will be randomized 1:1 to receive either Implementation as Usual (IAU) or IAU+EBIS. Randomization will take place after the informed consent process and prior to beginning either training condition.

4. Administration of Surveys and/or Process:

Aim 1: N/A

Aim 2: To accomplish Aim 2, we will deliver the draft version of EBIS as outlined in the procedures below. Following receipt of the draft version of EBIS, clinicians will complete brief 45-60 minute qualitative interviews with trained study staff. Qualitative interviews will take place via phone, videoconference, or in person, depending on participant preference.

Aim 3: During the clinical trial, all measures will be administered by trained research staff in accordance with the assessment schedule outlined above. Questionnaires at each time point will be administered either in paper format or electronically using REDCap, depending on participant preference (See *Study Instruments* above). Qualitative interviews will take place via phone, videoconference, or in person, depending on participant preference.

5. Data Management:

Drs. [name] (PI) and [name] (co-PI) will oversee all data cleaning and management with support from co-Investigator [name].

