In this prototyping phase, EBIS will be administered either individually to clinicians or in small groups of 2-4 clinicians. The syllabus that will guide EBIS administration is included for the IRB's review. All trainings and consultation sessions will be video recorded and transcribed using HIPAA compliant software. During administration, study staff will take field notes on implementation challenges. Clinicians will complete a brief demographic questionnaire before and after completing the training. After receiving EBIS, clinicians will complete brief qualitative interviews (45-60 minutes) about their experience with EBIS either virtually or at a private location (e.g., the University of Pennsylvania campus or your office location). Interviews will be audio-recorded and transcribed. The first part of the interview will query clinicians on acceptability and feasibility of EBIS. The second part will comprise semi-structured questions about perceptions of how EBIS influenced anxiety and self-efficacy to deliver the CSSRS and SPI. The last part will solicit suggestions for improvements to optimize EBIS. Clinicians will also receive continuing education credits for training activities. We anticipate it will take clinicians approximately 4-5 hours to complete study procedures (up to 4 hours of training and 1 hour for the interview).

We will make iterative refinements after each EBIS administration in response to observed implementation challenges and clinician feedback until saturation is reached (anticipated maximum: 20 clinicians). When clarity is needed on whether certain adaptations are needed, we will return to our Advisory Board for guidance.

The finalized manual that will guide EBIS administration in Aim 3 was submitted for the IRB's review.

Aim 3: Test acceptability, feasibility, and preliminary effectiveness of EBIS to target implementation mechanisms and outcomes relative to implementation as usual (IAU) via a pilot randomized trial.

After consenting, clinicians will be randomized to one of two implementation arms: IAU (n=20), or EBIS (n=20), which comprises all IAU activities plus EBIS as refined in Aim 2. If a clinician drops out of the study prior to attending their initial workshop (which is when official randomization will occur), we will make efforts to replace that individual to obtain a final sample of 40 clinicians randomized.

IAU Condition. Gold-standard IAU for SSAs typically comprises pre-implementation

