Quantitative analyses This pilot feasibility trial is not intended to be adequately powered to detect significant effects.^{94,95} Findings will provide key preliminary data to support the feasibility of EBIS and study procedures for a fully powered R01 (e.g., frequency of suicidal ideation over the 8-week follow-up period). Qualitative analysis of interview transcripts and mixed methods analysis will supplement quantitative analyses.

Preliminary Analysis. Data screening and missing data analysis will be conducted in accordance with best practice recommendations.⁹⁶ Prior to conducting main analyses, we will examine the psychometric properties of all scales used to assess constructs of interest (e.g., coefficient alpha) to confirm adequate performance. We will conduct analyses of baseline variables as a randomization check to ensure comparable baseline characteristics for clinicians in EBIS and IAU. Any differences will be controlled for in subsequent analyses.

Hypothesis 1: EBIS will be an acceptable and feasible implementation strategy. We will calculate descriptive statistics on the AIM and FIM measures and compare scores between EBIS and IAU. We will also evaluate EBIS feasibility by calculating the proportion of clinicians randomized to EBIS who complete all exposure tasks.

Exploratory Hypotheses 1 and 2: EBIS will engage target implementation mechanisms of clinician anxiety and self-efficacy better than IAU; clinicians randomized to EBIS will show improved SSAI adoption and fidelity relative to clinicians randomized to IAU. We will examine the effect of condition over time on target mechanisms (anxiety and self-efficacy) and implementation outcomes (mean CSSRS screening frequency across encounters, proportions of appropriate encounters in which clinicians conduct follow-up assessment with the CSSRS and SPI use, as measured by CSR, and average SPI fidelity scores on role plays) using repeated measures analysis of covariance (ANCOVA), controlling for organization (given the small sample size and that we will recruit from only a small number of organizations for this pilot, we do not anticipate the need for multilevel analysis).

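### SPI fidelity has no baseline score, and the plan fixes no prognostic covariate for it except organization; prior SPI training is the natural one to name in advance

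*Combined protocol and SAP*

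**What the plan says.** **Timing.** Study Instruments (Brief Role Plays) says the SPI role play is "coded for competence with the Safety Planning Intervention Rating Scale (SPIRS). This will be administered at Time 3 and Time 4". Table 2 agrees: the fidelity row is marked at T3 and T4 only. Anxiety, self-efficacy and SSAI use by chart-stimulated recall (CSR) all have a T1 value.

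**Population.** The Aim 3 note under Objectives says of the CSSRS and SPI, "which are currently already the recommended practice in many City of Philadelphia agencies". Key Exclusion Criteria adds: "Participants will not be excluded based on sex, demographics, and or past experience".

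**T1 data.** The Clinician Demographics entry covers "professional characteristics (e.g., years of experience, theoretical orientation, caseload descriptions", work setting and personal experience with suicide. Other T1 measures include self-efficacy for SSAI use, perceived knowledge, attitudes to safety planning, anxiety sensitivity, organizational capacity and CSR. No T1 entry names prior CSSRS or SPI training.

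**Allocation.** "Clinician participants will be randomized 1:1 to receive either Implementation as Usual (IAU) or IAU+EBIS". The planned arms are "IAU (n=20), or EBIS (n=20".

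**Analysis.** Statistical Analysis plans a repeated measures ANCOVA controlling for organization. A preliminary randomization check adds any baseline variable on which the arms differ. Neither a list of variables nor a threshold is given.

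**The concern.** Fidelity is the quantitative outcome least exposed to self-report. CSR is the clinician's own account, since staff never see the chart, and the other measures are questionnaires. Fidelity is also the one outcome for which the ANCOVA has no pre-training value to use.

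Without a baseline score, the usual substitute is a pre-randomization variable expected to predict the outcome. Whether a clinician had already been trained in the SPI is an obvious candidate, because the sample probably mixes trained and untrained clinicians. The plan does not name it. The organization term absorbs differences between agencies, but randomization is by clinician, so trained and untrained colleagues in one clinic can still split unevenly between arms.

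The indirect T1 proxies enter only through the randomization check. In a trial of 40 such a check rarely flags a moderate imbalance. When the arms happen to be balanced, it gives up the precision that a prognostic covariate would bring. At stake are the width of the fidelity interval and what the pilot can tell the planned R01 about whether prior training needs adjustment or stratification.

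**Working it through.** The documents give no SD, effect size, alpha or correlation for fidelity, so the plan has no figure to reproduce beyond 20 + 20 = 40. All trained shares and correlations below are assumptions.

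**1. Unadjusted precision.** With 20 per arm and outcome SD 1, ignoring organization:

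- 95% half-width = t(38; 0.975) × √(2/20) = 2.024 × 0.316 = 0.64 SD.

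**2. How unevenly prior training could fall.** Let K of 40 clinicians be trained and split them 20/20 at random, treating the 40 as one pool. The variance of the number trained in one arm is 20 × (K/40) × (1 − K/40) × 20/39. The SD of the arm difference in proportions is 2 × √variance / 20.

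| Trained (assumed) | Variance | SD of arm difference | P(difference ≥ 20 points) |
|---|---|---|---|
| K = 8 (20%) | 1.641 | 0.128 | 0.235 |
| K = 16 (40%) | 2.462 | 0.157 | 0.333 |

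The pool ignores organization. If training follows agency policy, part of this imbalance is already adjusted for, so these figures are upper-end.

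**3. Would the randomization check see it?** The plan gives no threshold; p<0.05 is assumed, with K = 16.

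- 10 vs 6 trained (20 points): Fisher p = 0.33, chi-square p = 0.20.
- 11 vs 5 trained (30 points): Fisher p = 0.11, chi-square p = 0.053.

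Neither is flagged, even if training is recorded. For a continuous T1 proxy, the imbalance must exceed 2.024 × 0.316 = 0.64 SD to be flagged.

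**4. What a 20-point imbalance does to the contrast.** For a yes/no item held by 40%, correlation r implies a trained-versus-untrained gap of r / √(0.4 × 0.6) = r / 0.490 outcome SDs. Multiplying by 0.20 gives the shift:

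- r = 0.1: 0.04 SD
- r = 0.3: 0.12 SD
- r = 0.5: 0.20 SD

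A full 1 SD gap corresponds to r = 0.49, the top of this range.

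**5. What adjustment buys.** The variance ratio is (1 − r²) × 36/35. Here 36 = 40 − 1 − 1 − 2 is the residual degrees of freedom with an intercept, arm and three organizations, and 35 is what remains after one covariate. Read r as the correlation that remains within organization. The half-width column applies the ratio to the 0.64 SD from step 1, as a guide to scale.

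| r (assumed) | Variance ratio | Change in variance | Half-width |
|---|---|---|---|
| 0.1 | 0.99 × 1.0286 = 1.018 | +2% | 0.65 SD |
| 0.3 | 0.91 × 1.0286 = 0.936 | −6% | 0.62 SD |
| 0.5 | 0.75 × 1.0286 = 0.771 | −23% | 0.56 SD |

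With five organizations the factor is 34/33, and the ratios become 1.020, 0.938 and 0.773. The conclusion does not change.

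**The case against.** **The item may already be collected.** The demographic list is introduced as examples and the approved form is not in the documents. This stands: a reader might infer that prior training goes unrecorded, but the documents show only that it is not named. The gap in the analysis does not depend on the form.

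**Incoming skill is not invisible.** A reader might infer that it stays wholly unadjusted and leaves no trace in the data. The documents do not support that. T1 self-efficacy, perceived knowledge, CSR-reported use and years of experience all bear on it, organization is in the model, and observed differences are to be controlled for. What remains is that these proxies are indirect, none is fixed in advance for fidelity, and the rule that admits them misses moderate imbalance.

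**Chance imbalance is already in the standard error.** This is correct. The contrast is unbiased over randomizations and the 0.64 SD half-width allows for such imbalance. The shifts in step 4 describe a particular realized allocation and are not a further error on top of the interval.

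**The correlation may be low.** Both arms receive SPI teaching and practice before the T3 role play, which may level earlier differences. Being a recommended practice also does not show that clinicians were trained. Both points stand, and they are why the range extends down to 0.1, where adjustment costs slightly more than it gains.

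**The outcome is secondary and the trial a pilot.** The plan says "This pilot feasibility trial is not intended to be adequately powered to detect significant effects", and the primary outcomes are acceptability and feasibility. This limits the weight of the point. It does not remove the case for a change this cheap in a study meant to inform a larger one.

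**Conclusion.** The point holds as an inexpensive improvement to a secondary, exploratory analysis; it does not show bias. The documents establish three things: fidelity has no T1 score, organization is its only covariate named in advance, and prior SPI or CSSRS training appears neither in the analysis nor among the T1 examples, in a population where it is likely to vary.

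The cost is modest. Adjustment would remove about 6% of variance at a correlation of 0.3 and 23% at 0.5, taking the half-width from 0.64 to 0.62 or 0.56 SD; at 0.1 it would add about 2%. A 20-point imbalance has a probability of 24% to 33% if 20% to 40% of clinicians are trained, before allowing for organization. In the worked 40% case, a check at p<0.05 would miss it. The trained share, the correlations and that threshold are assumptions, since the documents give none of them.

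**What to change.** 1. Confirm that the T1 form asks whether the clinician had formal SPI training before this study. If it does not, add that yes/no item.
2. In Statistical Analysis, pre-specify prior SPI training, with organization, as a fixed covariate in the T3 and T4 fidelity comparison, whether or not the arms differ on it.
3. If the item cannot be obtained for every clinician, pre-specify T1 self-efficacy for SSAI use for all of them instead. It is already collected. T1 CSR-reported SPI use is a weaker choice: it covers one clinic week and may mainly reflect whether an at-risk patient was seen. The protocol itself chose a 12-week follow-up to make at least one such encounter likely.

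The cost is at most one question and one model term. The downside is one degree of freedom and about 2% of precision (in variance) if the covariate turns out nearly unrelated to fidelity. A T1 role play would supply a true baseline, but it would add 45 to 60 minutes per clinician and give both arms practice before training, so it is not proposed here.

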preparation, didactic training, knowledge tests, experiential role plays, ongoing expert consultation, and providing certification status to clinicians who attain established benchmarks. Pre-implementation preparation will include provision of materials (e.g., SPI manual,⁷⁸ instructions,⁷⁹ and forms). Didactic training will occur in two parts: (1) CSSRS screening and assessment, and (2) SPI use. Part one will consist of materials we previously developed based on community clinician feedback. Part two will follow established SPI guidelines, including didactic training about SPI rationale and evidence base and experiential practice. IAU also will include supports for electronic health record integration (e.g., previously developed templates). After training, clinicians will receive six, one-hour sessions of expert consultation over the course of 12 weeks to discuss implementation barriers and receive more role play practice.

EBIS Condition. Clinicians randomized to EBIS will receive all IAU elements outlined above plus the exposure-based intervention described above and refined in Aims 1 and 2 (see **Table 1**).

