The time allotted for the training in Aim 3 will be standardized across conditions, but the content of the training will differ. Exact hours and time the training takes to complete may vary slightly depending on the number of clinicians in each training session, but the content of the training and the trainer will be the same for each session. As described throughout the protocol, the control training will we are using gold standard implementation as usual (IAU) training, role plays, and IAU-focused consultations. The intervention or EBIS condition would receive additional EBIS constructs in training (i.e., specific psychoeducation about how clinician anxiety is normal and to be anticipated in suicide prevention work), exposure-focused role plays (vs. traditional role plays in the IAU condition) and consultations (IAU = traditional consultation; EBIS = emotion-focused consultation). The training for both conditions will be led by [name], an expert in suicide prevention EBP implementation, and [name], a post-doctoral candidate, who will be trained and supervised by [name].

Participants will complete baseline surveys (30 min) and measures of SSAI use via chart-stimulated recall (CSR) (15 min) at T1 and then receive either IAU or EBIS. T2 assessment will comprise surveys (30 min) and will take place immediately after training in both arms. At T3 and T4 (two- and twelve-week follow-ups), clinicians will complete brief questionnaires (30 min), a CSR to measure SSAI use (15 min), and a role play to index SPI fidelity (45-60 min). At T4, clinicians will also complete a qualitative interview (30 min). We anticipate it will take clinicians approximately 17 hours to complete study procedures over 12 weeks (6 hours for training, 6 hours for expert consultation, and ~5 hours for research assessments across T1-T4).

Note: As Aim 3 activities meet the NIH definition of a clinical trial, Aim 3 activities are registered on ClinicalTrials.gov as a condition of award (NCT05172609).

2. Data Collection:

Not applicable.

3. Genetic Testing:

Not Applicable

4. Use of Deception:

No deception will be used in this project.

5. Statistical Analysis:

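### Does the protocol leave unclear whether the EBIS arm adds exposure work to IAU or replaces IAU role plays and consultation?

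*Combined protocol and SAP*

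**What the plan says.** Three places define the EBIS arm as an addition to IAU:

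- METHODS, 3. Method for Assigning Subjects to Groups: "Clinician participants will be randomized 1:1 to receive either Implementation as Usual (IAU) or IAU+EBIS".
- STUDY PROCEDURES, 1. Detailed Description, Aim 3, on the EBIS arm: "which comprises all IAU activities plus EBIS as refined in Aim 2".
- The EBIS Condition paragraph of the same section: these clinicians "will receive all IAU elements outlined above plus the exposure-based intervention".

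The IAU Condition paragraph lists "experiential role plays, ongoing expert consultation" among the IAU elements. It sets the consultation at "six, one-hour sessions of expert consultation over the course of 12 weeks", used for implementation barriers and further role play.

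Later in the Aim 3 description the tone changes: "The time allotted for the training in Aim 3 will be standardized across conditions, but the content of the training will differ". That paragraph then says the EBIS arm receives "additional EBIS constructs in training", and sets the two formats against each other: "exposure-focused role plays (vs. traditional role plays in the IAU condition) and consultations (IAU = traditional consultation; EBIS = emotion-focused consultation". One time budget of about 17 hours is given, not split by arm.

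**The concern.** Role plays and consultation are IAU elements that the EBIS arm is said to keep. The later paragraph appears to give each arm its own kind of role play and its own kind of consultation within a common time allowance. Read literally, that is substitution.

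The two readings answer different questions. If EBIS clinicians also receive the IAU role-play and consultation content, a difference between arms estimates the effect of adding EBIS to IAU. If they do not, it estimates an exposure-focused package against a traditional one at equal time, and a benefit of exposure could be offset by less SPI rehearsal. SPI fidelity is the outcome where this would show most, since it is scored on an SPI role play at T3 and T4. The BACKGROUND section says the data will inform a larger trial, which needs to know which contrast was piloted.

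**Working it through.** **1. Reproduce the time budget** (Detailed Description, Aim 3; minutes).

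| Time point | Components | Minutes |
|---|---|---|
| T1 | 30 + 15 | 45 |
| T2 | 30 | 30 |
| T3 | 30 + 15 + (45 to 60) | 90–105 |
| T4 | 30 + 15 + (45 to 60) + 30 | 120–135 |
| Sum | | 285–315, or 4.75–5.25 h |

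Adding 6 h of training and 6 × 1 h of consultation gives 16.75–17.25 h, which matches the stated 17 h. No separate block of time is set aside for EBIS.

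**2. Does equal training time imply that IAU content is displaced?** The hours of EBIS content in Aim 3 are not stated. Assume 0.5 to 2 h inside the 6 h of training. The time left for IAU content is then 6 − 0.5 = 5.5 h down to 6 − 2 = 4 h. The Aim 2 description gives a comparison: CSSRS training, SPI training and the EBIS prototype together take about 3–4 h. Aim 3 therefore allots 6 − 4 = 2 to 6 − 3 = 3 h more than that combined package needed. Even with 2 h of EBIS content, the remaining 4 h is no shorter than the whole Aim 2 package. Aim 2 used a prototype, so this does not prove what Aim 3 contains. It does show that a fixed 6 h does not force IAU content out. The comparison covers training only, because the Aim 2 figure has no counterpart to the six consultation hours.

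**3. Read the wording together.**

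| Element | Text suggesting replacement | Text suggesting addition |
|---|---|---|
| Training content | Same time, different content | EBIS constructs are called additional |
| Role plays | Exposure-focused set against traditional | Three arm definitions keep all IAU elements; SPI training includes experiential practice |
| Consultation | Emotion-focused set against traditional | The relapse-prevention part of the EBIS description says consultation will also take up anxiety and avoidance |

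A coherent reading is available. Both arms have role plays and consultation, and in the EBIS arm these carry an exposure or emotion focus. The EBIS description uses a trained actor for exposure practice, so one role play could serve both exposure and SPI rehearsal. The definitions promise elements, not equal minutes of each.

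**4. What depends on the answer?** The comparison of the two packages as randomized and delivered is valid under both readings. The primary outcomes, acceptability and feasibility, refer to whichever condition the clinician received. The statistical section already says the pilot is not powered. For scale, with 20 per arm, full retention, one time point and a normal approximation, the 95% half-width for a standardized difference is 1.96 × √(1/20 + 1/20) = 0.62 SD. A null on SPI fidelity could not be taken as absence of benefit under either definition.

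**5. Can the delivered content be recovered?** The Aim 3 procedures have all training and consultation video recorded in both arms. The confidentiality section has recordings transcribed and the de-identified transcripts stored. The Detailed Description also says that a finalized Aim 3 manual went to the IRB. That manual is not among these documents.

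**The case for a change.** The strongest case for acting is that three definitions say one thing, a fourth description uses the language of alternatives, and the single budget shows no added time. Each consultation hour is fixed, so minutes spent on clinician anxiety must come from something else. No passage says that exposure-focused role plays rehearse the SPI steps, or that emotion-focused consultation keeps the IAU agenda. A clarifying sentence would cost almost nothing, and a pilot exists to inform the next trial.

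Part of this stands. The wording is uneven, and the EBIS arm may well get fewer minutes of traditional role play and consultation than the IAU arm. But the documents show neither that any IAU element is dropped nor how many minutes move. All six consultation hours, half of the 12 contact hours, fall under the contrasting description; that measures how much text is affected, not how much practice is lost. That SPI fidelity would suffer most is an inference. The need of the later trial is real, but the manual and transcripts are better sources for it than another protocol sentence.

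**Conclusion.** No change to the plan follows. The inconsistency is one of wording, of low severity, and is held with moderate confidence. Resolving it would write down an arm definition without altering randomization, the 20 per arm, the assessments, the repeated-measures ANCOVA or any result. The amount of IAU practice displaced cannot be derived from the documents and may be zero.

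This rests on three assumptions: that the finalized manual sets out the content of the EBIS role plays and consultation; that transcripts from both arms are kept as described; and that the report describes each arm as delivered. If the manual shows that IAU content was retained, the exploratory contrast is EBIS added to IAU. If it shows replacement, the contrast is an equal-time package comparison and would be reported under that name. Either way, the choice concerns how a result is labelled, and a sensible analyst would make it at the reporting stage.
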